Study Title: Feasibility of the Camp Power Up Program on Children's Body Weight and Quality of Life

NCT #: NCT03235440

Document date: September 1, 2020

PBRC Institutional Review Board
Federal Wide Assurance 00006218
IRB Registration 00000708

PBRC IRB # 2017-014

Acronym: Power Up

PROTOCOL TITLE: "Camp Power Up"

PRINCIPAL INVESTIGATOR:

[name].

MEDICAL INVESTIGATOR:

[name].

FUNDING SOURCE: Institutional funds

DATE: 08/26/2020

IRB Review History: Submission # 4

Objectives

The objective of this study will be to evaluate the effects of a one week weight management summer camp on children's weight, self-reported health behaviors, quality of life, mood and feelings, self-esteem, weight management efficacy, enjoyment of physical activity, and body image. Children will also report acceptability and enjoyment of technology-supported physical activity options, specifically the HD Expresso stationary bicycles ("cybercycling").

Background

Obesity affects 17% of children and adolescents in the U.S.¹ Children are entrenched in an obesogenic environment, often with little support in the home, school, or medical environment to make healthy choices. Obesity is increasingly common in underserved communities that lack access and resources for physical activity and healthy eating. Louisiana is a prime example of the need for effective obesity treatment, ranking 1st nationally for adult obesity and 4th for adolescent obesity with the highest obesity prevalence among African American adolescents.¹ We urgently need evidence-based

programs to help children and families change lifestyle behaviors, achieve clinically significant weight loss, and thereby reduce the prevalence of pediatric obesity.

The U.S. Preventive Services Task Force identifies behavioral treatment including dietary, physical activity, and behavioral counseling components as a viable option for pediatric obesity treatment,² yet a key challenge is how to implement these programs to maximize access and participation. Summer (between school years) represents an opportunity for intensive intervention to change health behaviors and help children to lose weight. During the summer months, children gain weight at a more rapid pace^{3,4} and spend more time engaged in sedentary behavior⁵ compared to the school year. The American Diabetes Association launched Camp Power Up as a summer week-long day camp for youth who are obese and/or at high risk for developing type 2 diabetes. The camp will focus on wellness education, nutrition, physical activity, and obesity prevention. The purpose of the proposed study is to examine effects of Camp Power Up on children's weight status and their psychosocial health.

Inclusion and Exclusion Criteria

Children must meet the following eligibility criteria to participate in the study:

- Aged 6 to 14 years
- Enrolled in the ADA Camp Power Up

Number of Subjects

We plan to enroll up to 62 participants total. A total of 12 participants were enrolled in summer 2017 and an additional 50 are anticipated for summer 2018.

Recruitment Methods

All children selected to participate in the ADA summer camp program will be asked to participate in this study. The ADA anticipated enrollment of approximately 50 children for the one week session each summer (summer 2017, summer 2018). Recruiting efforts include, but are not limited to the institution's email listserv, social media posts, and flyer drops.

Study Timelines

The enrollment and participant's participation in the study will last approximately one week (five daytime sessions). The primary analyses will be completed by January 1, 2018 for the summer 2017 camp. The primary analyses for the summer 2018 camp will be completed by January 1, 2019.

Study Endpoints

AIM 1: Evaluate the effects of a one-week obesity prevention summer camp on children's weight, self-reported health behaviors, quality of life, mood and feelings, self-esteem, weight management efficacy, enjoyment of physical activity, and body image. Difference scores will be calculated between initial and final assessment, and effect sizes will be calculated using linear mixed models to determine clinical significance of weight-related and psychosocial changes throughout the program.

AIM 2: Examine the acceptance and feasibility of implementing the program at Pennington Biomedical Research Center's TReCC.

Acceptance and feasibility will be assessed by the number of participants enrolled and the number of camp sessions attended. Cybercycling acceptability and enjoyment will be assessed by a survey administered to the child after cybercycling for about 15 minutes.

Endpoints

The primary endpoint is the change in body weight. The secondary endpoints include self-reported changes in health behaviors, quality of life, mood and feelings, self-esteem, weight management efficacy, enjoyment of physical activity, and body image, as well as acceptability/enjoyment of cybercycling.

Procedures Involved

All participants will be explicitly told that their participation is voluntary and that they may terminate their participation at any time.

Consent and Assent Process. Informed consent for the child will be obtained from one of the participant's parents/legally authorized representatives prior to conducting any study procedures. The parent/legally authorized representative will be given an informed consent form to read and sign indicating their permission to allow their child to participate in the study. Parents will return this consent form to the study staff before the child's first visit. Because there is not a greater than minimal risk, informed consent will be obtained from one parent even if the other parent is alive, known, competent, reasonably available, and shares legal responsibility for the care and custody of the child.

Participants 12 years of age and older will be given a written assent form to read and sign before participating in any study procedures. Participants 6-11 years of age will be read an assent script and asked to verbally assent before participating in any study procedures. Participants 9-11 years of age with a high reading comprehension and maturity level may give written assent, rather than verbal assent, if deemed appropriate by the investigator or research staff member performing the assent. The study procedures will be explained using age appropriate terms, and children will be given the opportunity to ask questions about the study.

Parent survey. Parents will be asked to complete a questionnaire that will provide information on the child's sociodemographic characteristics, including sex, date of birth, and parents' marital status, highest level of education, family income, occupation, and employment status, as well as brief medical history. Parents will report their own height, weight, age, and sex.

Anthropometric measurements. Height and weight of each child will be measured in a private setting with the child dressed in light clothing. Height will be measured to the nearest 1.0 cm using a portable stadiometer. Weight will be measured to the nearest 0.1 kg using high-precision electronic scale. Percent body fat will be recorded from this scale. Body mass index (BMI) z-score will be calculated based on the child's age, sex, height, and weight, then compared to the 2000 Centers for Disease Control and Prevention (CDC) Growth Charts to calculate percentile and z-score.

Surveys. A pre-test and post-test psychosocial questionnaire will be completed by each participant at the beginning (session 1 or orientation) and end (session 5) of the program. The questionnaire will collect information about lifestyle, including diet and physical activity habits, media use, and sleep.

During summer 2017 camp only, children will be asked to complete a friendship nomination survey at the start and end of the 5-day ADA camp. On day 1, each child will be asked whether they know any other child participating in the camp. On day 5, another friendship nomination survey will be completed detailing the friends that the child met during the course of the camp. These friendship nomination data will be used to provide a longitudinal illustration of the ego-centric and overall social network developed during the span of the camp. This friendship nomination method has been used in the National Longitudinal Study of Adolescent Health, a nationally representative study in which one of the primary aims were to measure the association between adolescent social contexts and health and well-being. The survey questions will be from the following validated scales:

Impact of Weight on Quality of Life (IWQOL-Kids) (Summer 2017 only): The IWQOL-Kids is a 27-item measure of weight-related quality of life. Each item begins with the phrase, “Because of my weight,” and contains five response options, ranging from “always true” to “never true.” In addition to a total score, there are scores on four domains: Physical Comfort, Body Esteem, Social Life, and Family Relations. Scores range from 0–100, with higher scores representing better quality of life. The IWQOL-Kids has demonstrated good internal consistency, as well as sensitivity and responsiveness.^{6,7} The IWQOL-Kids will be administered to participants aged 11 and older.

PedsQL (Summer 2017 and 2018): The PedsQL is a general health related quality of life self-report measure with complementary scales for children (ages 6–14).⁸ The measure assesses physical, emotional, social, and school functioning, and provides a psychosocial summary score as well as a total score. Scores range from 0–100, with higher scores representing better quality of life. The PedsQL has been shown to be both reliable and valid in this age range.⁸

Weight Efficacy Lifestyle questionnaire (WEL; Summer 2017 and 2018): The WEL assesses self-reported eating habits and perceived self-efficacy in regards to eating and weight loss.⁹ The WEL consists of 20 items designed to measure five hypothetical dimensions of efficacy for weight management: availability, negative emotions, physical discomfort, positive activities, and social pressure. The items were slightly reworded to make them easily understandable to a pre-adolescent population. Good reliability and validity have been reported for the WEL in adult populations^{9,10} and adequate scale reliability in children ($\alpha=0.94$).¹¹

The Physical Activity Enjoyment Scale (PACES; Summer 2017 and 2018): The PACES is a 16-item measure of enjoyment during physical activity.¹²

The Body Image Assessment of Preadolescents (BIA-P; Summer 2017 only): The BIA-P is a reliable and valid measure of body image in children ages 6 to 14.^{13,14}

During summer 2018 camp only, children will be allowed to use the HD Expresso cybercycling stationary bicycles in the TReCC for 15 minutes each. Afterwards, they will complete a brief survey on their enjoyment and acceptability of the cybercycling.

(Summer 2018) One month after the conclusion of the camp, an optional post-camp celebration will be hosted at a local community center for all parents and camp participants. Participants' height and weight will be measured. Participants will be asked to complete a brief survey.

The following is the train schedule for procedures:

	PRE-VISIT	V1 Day 1	V2 Day 5	1 month Post- Visit
Consent	x			
Parent Questionnaire	x			
Assent	x			
Height		x	x	x
Weight		x	x	x
Child Questionnaires		x	x	x

Power analysis.

Difference scores will be calculated between initial and final assessment, and effect sizes will be calculated using linear mixed models to determine clinical significance of weight-related and psychosocial changes throughout the program. Acceptance and feasibility will be assessed by the number of participants enrolled and the number of camp sessions attended.

Data and Specimen Management

The Pediatric Obesity and Health Behavior Laboratory, supervised by [name], will have primary responsibility for data collection, data management, manual data entry, and data analysis. All electronic data will be stored in the secure Pennington database, with access given to only necessary, HIPAA-certified staff. All hard copies of data will be stored in a secure, locked cabinet at Pennington Biomedical Research Center. Access to data files can be made only with permission of the Academic Principal Investigator. Data will be stored for 5 years following study completion.

Provisions to Monitor the Data to Ensure the Safety of Subjects

This study does not involve more than minimal risk to participants. All data will be collected through non-invasive observations or surveys.

Withdrawal of Subjects

Participation is voluntary, so participants may withdraw from the program at any time. During the program, participants may be withdrawn from the program due to the unwillingness of the child/adolescent or the parent/legally authorized representative to cooperate with the study staff. Data that have already been collected during the course of the study from a withdrawn participant will be used, unless a specific request is otherwise received.

Risks to Subjects

The study contains no foreseeable risks, discomforts, or hazards to participants or family members.

Potential Benefits to Subjects

There is no direct benefit for the participant.

Vulnerable Populations

The ADA Power Up program will involve children as participants (6-14 years of age). As such, their parents and/or legally authorized representative will provide written informed consent allowing their child to participate in the study. In addition, participating children will provide verbal or written assent (depending on age and maturity level).

All participants will be explicitly told that their participation is voluntary and that they may terminate their participation at any time. If a participant indicates that they wish to stop participating, all study procedures they are undertaking at that time will be stopped to protect their rights and welfare.

Sharing of Results with Subjects

Individual participant results will be provided if the participant or parent requests them. Results from the study will be submitted for manuscripts in scholarly journals and presentations. All study reports for publication will present only aggregated data to minimize the risks that a participant can be identified from their participation in the study.

Setting

Program sessions will take place primarily at the TReCC or in the Conference Center. Anthropometry will be measured in the TReCC anthropometry room or in the Conference Center in private classrooms. The outpatient clinic and anthropometry room will be used as a back-up location if required.

Resources Available

Pennington Biomedical is a model for clinical research, since it houses basic, clinical and population research programs in one facility. TReCC is well-equipped to administer and support this study. Program-related assessments will be completed in TReCC, which has all the necessary equipment needed to perform the procedures described herein. The program personnel are highly qualified with extensive diabetes and obesity-related backgrounds and experience conducting research involving human participants, both here at Pennington Biomedical, and at other institutions.

Compensation

Subjects will not be compensated for participation in the study.

Confidentiality

All data collected in this project will be subject to the same confidentiality requirements that are in place for our other studies at the Pennington Biomedical. Study files will be kept in locked cabinets and access restricted to program staff. Personal identifiers are not included in computer files. No individual's data will be released without their specific written consent. Research staff, members of the Institutional Review Board, and personnel in charge of maintaining data security from the Pennington Biomedical Research may inspect and/or copy the medical records related to the study. Results of the study may be published; however, names and other identifying information will be kept private. Other than as set forth above, the participant's identity will remain confidential unless disclosure is required by law.

Provisions to Protect the Privacy Interests of Subjects

Privacy in the context of this study includes confidentiality of data and personal information. During interviews, measurements, and program sessions, the program staff will ensure full privacy of participants and will ensure that the data are stored in a secured area. Participant weight measurements will be conducted individually in private to protect the privacy interest of the subject.

Compensation for Research-Related Injury

No form of compensation for medical treatment or for other damages (i.e., lost wages, time lost from work, etc.) will be available for this research study. In the event of injury or medical illness resulting from the research procedures, participants will be referred to a treatment facility.

Economic Burden to Subjects

Participants and participating families will be required to bear the cost of transportation to and from all camp and study sessions.

Consent Process

Informed consent and assent will be obtained prior to conducting any program procedures. Because there is not a greater than minimal risk, informed consent will be obtained from one parent even if the other parent is alive, known, competent, reasonably available, and shares legal responsibility for the care and custody of the child. The study procedures will be explained to parent(s) and prospective participants (6-14 years of age). The parent/legally authorized representative and prospective participant will be asked if they have any questions about the study. The parent/legally authorized representative and prospective participant will be offered a waiting period between informing the prospective participant and obtaining the consent. When the parent/legally authorized representative and prospective participant are both ready, the informed consent process will then proceed as follows.

For participants 12-14 years of age:

- Parent/legally authorized representative will be given an informed consent form to read and sign indicating their permission to allow their child to participate in the study.

- Following the obtainment of written parental consent, participants 12 years of age will be given a written assent form to read and sign before participating in any study procedures.

For participants between 6-11 years of age:

- Parent/legally authorized representative will be given an informed consent form to read and sign indicating their permission to allow their child to participate in the study.

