Study Title: Feasibility of the Camp Power Up Program on Children's Body Weight and Quality of Life

NCT #: NCT03235440

Document date: September 1, 2020

We used SPSS to conduct paired t-tests to analyze any pre-to-posttest changes in health behaviors and psychosocial well-being outcomes. Cohen's d was computed as effect size to interpret the between time differences. Subsequently, we conducted repeated measure multivariate analyses of variance (RM-MANOVAs) to examine pre-to-posttest changes in health behaviors and psychosocial well-being outcomes by gender (boys vs. girls) and household income (\$50,000 as the split value). We further explored the pre-to-posttest changes in the outcomes (using gain scores: posttest – pretest data) by weight status (normal weight, overweight, obesity), but did not perform inferential statistical analysis due to the uneven sample sizes between the weight groups. Descriptive results including both raw and estimated marginal means were obtained to quantify and visualize group differences. Partial eta square (η^2) was reported as effect size from results from the RM-MANOVAs, while significance level was set to be $\alpha = 0.05$.

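### The SAP contains no analysis of change in body weight, the protocol's primary endpoint; its tests cover only outcomes the protocol ranks as secondary

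*Protocol*

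**What the plan says.** **Protocol.** The Endpoints section is explicit: "The primary endpoint is the change in body weight". It then ranks the rest: "The secondary endpoints include self-reported changes in health behaviors, quality of life, mood and feelings, self-esteem, weight management efficacy", followed by enjoyment of physical activity, body image, and acceptability of cybercycling. AIM 1, under Study Endpoints, plans difference scores from initial to final assessment and effect sizes from linear mixed models "to determine clinical significance of weight-related and psychosocial changes throughout the program". The Power analysis section repeats this plan and gives no numbers. Weight is to be recorded to 0.1 kg (Anthropometric measurements) and is scheduled at Day 1, Day 5 and one month after camp (schedule under Procedures Involved).

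**SAP.** The SAP is one paragraph under the study title, "Feasibility of the Camp Power Up Program on Children's Body Weight and Quality of Life". It describes:

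- Paired tests: "We used SPSS to conduct paired t-tests to analyze any pre-to-posttest changes in health behaviors and psychosocial well-being outcomes". The effect size is stated next: "Cohen's d was computed as effect size to interpret the between time differences".
- Repeated-measures MANOVAs "to examine pre-to-posttest changes in health behaviors and psychosocial well-being outcomes by gender (boys vs. girls) and household income".
- Gain scores "by weight status (normal weight, overweight, obesity), but did not perform inferential statistical analysis".

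The significance level is 0.05. The paragraph does not name body weight, BMI or BMI z-score as an outcome.

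**The concern.** A SAP should first say how the primary endpoint will be estimated. This one assigns its tests, effect sizes and significance level to outcomes the protocol places in the second tier, and is silent on the first. A reader who follows it would obtain no estimate of weight change, no interval and no test. The practical danger is that significant psychosocial or behavioral changes come to stand in for the result on weight. No results report is among the documents, so this is a risk and not something shown to have happened.

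**Working it through.** The plan gives no figure to reproduce. The check compares the endpoint hierarchy with each analysis in the SAP.

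**1. Outcome of each SAP analysis**

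| SAP analysis | Outcome | Role of weight | Test? |
|---|---|---|---|
| Paired t-tests, Cohen's d | Behavioral and psychosocial | None | Yes |
| RM-MANOVAs by gender and income | Same two families | None | Yes |
| Gain scores by weight status | The outcomes already named | Grouping variable | No |

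Body weight is an outcome in 0 of 3 sets, and in 0 of the 2 with a test.

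**2. Could health behaviors include weight?** No. The protocol's Objectives and AIM 1 list weight and self-reported health behaviors as separate items, and Endpoints puts them in different tiers. Weight is measured on a scale, not self-reported.

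**3. Could the gain scores include weight?** In context, the outcomes there are the two families already named. Even on a generous reading, that step is descriptive within weight groups and gives no overall estimate, interval or test.

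**4. Could text have been removed?** Nothing in the SAP paragraph is marked as redacted.

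**5. Does the change of method matter as well?** Much less. With two visits and complete data, a random-intercept model with a visit effect returns the paired mean change. A simulation illustrates this. Its inputs are assumptions and not trial data: 12 + 50 children, baseline weight 60 kg (SD 15), true change -0.2 kg in 2017 and -0.6 kg in 2018, SD of change 0.8 kg.

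- Paired mean change: -0.5668 kg, SE 0.0968.
- Mixed model with visit and camp year: visit coefficient -0.5668, SE 0.0968.
- Visit-by-year term added: visit coefficient -0.1451, which is the 2017 camp alone; the 2018 change is -0.1451 - 0.5228 = -0.668.

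The two methods agree on the overall change. Once the interaction is in the model, the visit coefficient is no longer that overall change.

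**6. Pooled or by camp?** Number of Subjects gives 12 children enrolled in 2017 and 50 anticipated in 2018. If all 62 supplied both weights, the pooled mean change would be weighted 12/62 = 19% to 2017 and 50/62 = 81% to 2018. Study Timelines dates the primary analyses separately for each camp, so the choice needs to be stated. These weights bear on the repair and do not measure the defect.

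**The case against.** The strongest reply is that the primary endpoint is not without a plan: AIM 1 and the Power analysis section cover weight-related change, the measurement is specified, and the visits are scheduled. This stands, and it limits the point to the SAP. It does not remove it. The SAP is the document that sets out the analysis, and it carries over neither the outcome nor the model.

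Other objections, and what remains of each:

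- **This is a small, one-week feasibility study with no comparator, power figure or success criterion.** That is a reason to prefer estimation to testing. It is not a reason to omit the endpoint the protocol calls primary.
- **The title naming body weight is the study's title, shared with the protocol.** Correct. It is not evidence that the SAP promised a weight analysis, and the conclusion does not rely on it.
- **The SAP's outcomes cannot be matched one by one to the protocol's list.** Also correct. The SAP names only two families, and the protocol's list of eight secondary items is open-ended. Cybercycling acceptability is surveyed after the ride, with no pretest described, so at most seven listed items could enter a pre-post test. Matching the families to the secondary tier is an inference, but a safe one.
- **The protocol says only linear mixed models and names no terms.** True, so any particular specification is a proposal. In the simulated complete data, dropping camp year left the visit estimate and its SE unchanged.
- **The SAP is in the past tense and dated September 1, 2020, after both planned analysis dates (January 1, 2018 and January 1, 2019).** An addition can therefore correct the record, but it cannot make newly chosen model details prespecified.

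**Conclusion.** The concern holds, and the SAP is wrong as written on this point. It gives the one primary endpoint no analysis: 0 of its 3 sets of analyses, and 0 of its 2 sets of tests, have body weight as the outcome. The conclusion rests on the wording of the two documents and not on any assumed number; the simulation and pooling weights matter only for designing the repair. The missing outcome is the material gap. Replacing the mixed model with paired tests is a lesser departure. This must be corrected, because without it the SAP does not answer the protocol's main question. Confidence is high.

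**What to change.** Revise the SAP as follows.

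1. Make mean change in body weight (kg) from Day 1 to Day 5, with a 95% confidence interval, the first and primary analysis. Day 5 fits the one-week participation in Study Timelines, and it is the only post-camp weight scheduled for both camps.
2. Use the protocol's linear mixed model. A suitable form has visit and camp year as fixed effects, a random intercept per child, and all children with at least one weight.
3. State whether the pooled or the by-camp estimate is primary. Report each camp year separately, by camp or from a second model with a visit-by-year term. Leave that term out of the pooled model, or use an explicit contrast.
4. Treat the one-month weight as supplementary, since the celebration is optional and held only in 2018.
5. Label the behavioral and psychosocial results as secondary.
6. Identify the endpoint and the mixed-model approach as protocol-specified, and mark as post hoc only the model details fixed after the data were analyzed.

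The cost is SAP wording, one primary model and a by-camp breakdown, on weights already scheduled. No further children or measurements are needed. The downsides are the post hoc note and an imprecise estimate for the 12 children of 2017.

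### Does recording height only to the nearest centimetre damage the Day 1 to Day 5 comparison?

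*Protocol*

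**What the plan says.** Under Procedures Involved, the Protocol's paragraph on anthropometric measurements sets two resolutions: "Height will be measured to the nearest 1.0 cm using a portable stadiometer" and "Weight will be measured to the nearest 0.1 kg using high-precision electronic scale". BMI is formed from these, "then compared to the 2000 Centers for Disease Control and Prevention (CDC) Growth Charts to calculate percentile and z-score". The schedule table in the same section lists height and weight on Day 1, on Day 5 and at one month. The one-month visit is described as an optional gathering after the 2018 camp, at which "height and weight will be measured". No text says which height enters a BMI or z-score for a given day.

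The Endpoints section says: "The primary endpoint is the change in body weight". The secondary endpoints listed there are self-reported or psychosocial measures and the cybercycling survey. BMI, percentile and z-score are not among them. The Background describes the purpose more loosely, as effects on children's "weight status and their psychosocial health".

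The SAP opens: "We used SPSS to conduct paired t-tests to analyze any pre-to-posttest changes in health behaviors and psychosocial well-being outcomes". It then describes RM-MANOVAs of the same outcomes by gender and household income. Its only use of weight status is a three-group descriptive display of gain scores, without inferential testing.

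**The concern.** The two resolutions look mismatched. BMI depends on height squared, so one centimetre matters far more than one weight step. Children do not grow measurably between Day 1 and Day 5, so a difference between the two recorded heights is essentially error. A child whose true height lies near a half-centimetre can be recorded a full centimetre taller or shorter on Day 5 and appear to have changed BMI with no change in weight.

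If such changes were analysed with each day's own height, the result would be less precise than the weight readings allow. Finer recording would reduce the loss, and one height per child for both days would remove it. Children near a cut-off could also be put in the wrong weight-status group.

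**Working it through.** **Inputs from the documents.** Height step 1.0 cm and weight step 0.1 kg (Protocol, Procedures Involved); up to 62 children (Protocol, Number of Subjects). The documents give no SD, effect size or power figure, so there is no stated figure to reproduce.

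**Assumptions.** Children of 140 cm/50 kg, with 120 cm/30 kg and 160 cm/80 kg for range; repeat-measurement SD of height 0.1 to 0.3 cm per visit; SD of true weight change 0.5 to 1.0 kg.

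**Step 1: effect of one centimetre.** BMI = w/h², so a height error Δh shifts BMI by about 2Δh/h as a fraction. In weight terms this is 2wΔh/h:

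- 120 cm/30 kg: 2 × 30/120 = 0.50 kg per cm
- 140 cm/50 kg: 2 × 50/140 = 0.71 kg per cm
- 160 cm/80 kg: 2 × 80/160 = 1.00 kg per cm

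The weight step is 0.1 kg, and rounding weight at both visits gives an SD of 0.1 × √(1/6) = 0.041 kg. The apparent mismatch is real.

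**Step 2: noise in a five-day change if each day's own height is used.** Rounding errors at the two visits are not independent, because the same child is measured twice. With no repeat error both readings round alike and the noise is exactly zero. The figures therefore come from simulation (140 cm/50 kg, true height uniform within the centimetre):

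| Repeat-error SD (cm) | Children with a false difference of 1 cm or more | Noise SD, 1.0 cm recording (kg-equiv.) | Noise SD, 0.1 cm recording | Noise SD, one shared height |
|---|---|---|---|---|
| 0.1 | 11% | 0.240 | 0.105 | 0 |
| 0.2 | 23% | 0.340 | 0.204 | 0 |
| 0.3 | 34% | 0.419 | 0.304 | 0 |

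The mean spurious BMI change was zero to within simulation error (at most 0.0004 kg/m²), so a group mean is not biased.

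**Step 3: effect on a group mean.** The noise component of the standard error with 62 children is noise/√62: 0.240/7.87 = 0.030, 0.340/7.87 = 0.043 and 0.419/7.87 = 0.053 kg-equivalent. In the least favourable case at this body size (weight-change SD 0.5 kg, repeat-error SD 0.3 cm), the total standard error is √(0.5² + 0.419²)/7.87 = 0.083. With 0.1 cm recording it is √(0.5² + 0.304²)/7.87 = 0.074. Part of the excess is ordinary repeat error, which finer recording does not remove.

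**Step 4: where height enters the plan.**

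| Analysis | Uses height? |
|---|---|
| Primary endpoint, body weight | No |
| Secondary endpoints | No |
| SAP paired t-tests | No |
| SAP RM-MANOVAs by gender and income | No |
| SAP weight-status groups (descriptive) | Presumably, through BMI level |
| Five-day BMI, percentile or z-score change | Would, but not named as an endpoint or a test |

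**Step 5: weight-status groups.** Take an equal mix of 118 cm/28 kg, 140 cm/50 kg and 160 cm/80 kg, an assumed SD of log BMI of 0.15 to 0.25, and several assumed cut-off positions. A single height to 1 cm then puts 0.3 to 1.4 of 62 children in the wrong group, and a single height to 0.1 cm puts 0.1 to 1.0 there. Compared setting by setting, the difference due to coarser rounding is about 0.1 to 0.75 child. Growth-chart values are not in the documents, so noise on the percentile and z-score scales was not computed.

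**The case for a change.** The best case for acting is that BMI change is a foreseeable output. The Protocol commits to z-scores, the Background speaks of weight status, the aims and the Power analysis section promise effect sizes for weight-related changes, and re-measuring height on Day 5 serves no purpose for body weight alone. On this view the plan leaves a derivation choice open, and a short rule using one height per child would remove the five-day height noise at almost no cost. At some body sizes the loss is not trivial: with 160 cm/80 kg children and a weight-change SD of 0.5 to 1.0 kg, rounding alone would widen the smallest detectable change by 4% to 20%.

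The observation stands: the choice of height is unwritten, and anyone reporting a five-day BMI-based change should say which height was used. The rest does not carry over to this plan. Calculating a z-score is not a commitment to test its change, and the weight-related wording is met by body weight itself. The detectable-change percentages match no planned test and no stated power. The 20% end pairs the heaviest assumed child with the smallest assumed spread of weight change. Recording to 0.1 cm could help only a further camp, and none is described: the timelines cover 2017 and 2018, and the SAP is written in the past tense.

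**Conclusion.** The concern is arithmetically sound but does not call for a change. Centimetre recording affects no named endpoint and no test in the SAP. It could blur only a five-day BMI-based change, which the plan does not set out to analyse, and only if each day's own height were used; the documents do not show that it was. Even then the noise has mean zero and adds 0.03 to 0.05 kg-equivalent to the standard error with 62 children, assuming 140 cm/50 kg and a repeat-error SD of 0.1 to 0.3 cm. In the descriptive weight-status groups, rounding accounts for less than one child of 62 under the assumed BMI spread and cut-offs. An analyst can settle which height to use, and report it, if such a result is ever presented. These figures should not be read as a loss of power for this trial.
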